# **4.1.2** Serious Adverse Event Definition

Serious adverse event (SAE) means any untoward medical occurrence that at any dose:

- Results in **death**.
- Is **life-threatening** (refers to an AE in which the patient was at risk of death at the time of the event. It does not refer to an event which hypothetically might have caused death if it were more severe).
- Requires inpatient hospitalization or prolongation of an existing hospitalization (see clarification below on planned hospitalizations in Section Error! Reference source not found.).
- Results in **persistent or significant disability or incapacity**. (Disability is defined as a substantial disruption of a person's ability to conduct normal life functions).

- Is a congenital anomaly/birth defect.
- Is a **medically important event**. This refers to an AE that may not result in death, be immediately life threatening, or require hospitalization, but may be considered serious when, based on appropriate medical judgment, may jeopardize the patient, require medical or surgical intervention to prevent 1 of the outcomes listed above, or involves suspected transmission via a medicinal product of an infectious agent. Examples of such medical events include allergic bronchospasm requiring intensive treatment in an emergency room or at home, blood dyscrasias or convulsions that do not result in inpatient hospitalization, or the development of drug dependency or drug abuse; any organism, virus, or infectious particle (eg., prion protein transmitting Transmissible Spongiform Encephalopathy), pathogenic or nonpathogenic, is considered an infectious agent. Examples of such medical events include allergic bronchospasm requiring intensive treatment in an emergency room or at home, blood dyscrasias or convulsions that do not result in inpatient hospitalization, or the development of drug dependency or drug abuse; any organism, virus, or infectious particle (eg. prion protein transmitting Transmissible Spongiform Encephalopathy), whether pathogenic or non-pathogenic, is considered an infectious agent.
- Clarification should be made between a serious AE (SAE) and an AE that is considered severe in intensity (Grade 3 or 4), because the terms serious and severe are NOT synonymous. The general term *severe* is often used to describe the intensity (severity) of a specific event; the event itself, however, may be of relatively minor medical significance (such as a Grade 3 headache). This is NOT the same as *serious*, which is based on patient/event outcome or action criteria described above, and is usually associated with events that pose a threat to a patient's life or ability to function. A severe AE (Grade 3 or 4) does not necessarily need to be considered serious. For example, a white blood cell count of 1000/mm³ to less than 2000 is considered Grade 3 (severe) but may not be considered serious. Seriousness (not intensity) serves as a guide for defining regulatory reporting obligations.

# 4.1.3 Serious Adverse Event Reporting (SAE) Reporting

An adverse event or suspected adverse reaction is considered "serious" if, in the view of either the investigator or the sponsor, it results in any of the following outcomes:

Death

- A life-threatening adverse drug experience any adverse experience that places the patient, in the view of the initial reporter, at immediate risk of death from the adverse experience as it occurred. It does not include an adverse experience that, had it occurred in a more severe form, might have caused death.
- Inpatient hospitalization or prolongation of existing hospitalization
- A persistent or significant incapacity or substantial disruption of the ability to conduct normal life functions.
- A congenital anomaly/birth defect.

Important medical events that may not result in death, be life-threatening, or require hospitalization may be considered a serious adverse drug experience when, based upon appropriate medical judgment, they may jeopardize the patient or subject and may require medical or surgical intervention to prevent one of the outcomes listed in this definition. Examples of such medical events include allergic bronchospasm requiring intensive treatment in an emergency room or at home, blood dyscrasias or convulsions that do not result in inpatient hospitalization, or the development of drug dependency or drug abuse (21 CFR 312.32).

- Important medical events as defined above, may also be considered serious adverse events. Any important medical event can and should be reported as an SAE if deemed appropriate by the Principal Investigator or the IND Sponsor, IND Office.
- All events occurring during the conduct of a protocol and meeting the definition of a SAE must be reported to the IRB in accordance with the timeframes and procedures outlined in "The University of Texas M. D. Anderson Cancer Center Institutional Review Board Policy for Investigators on Reporting Serious Unanticipated Adverse Events for Drugs and Devices". Unless stated otherwise in the protocol, all SAEs, expected or unexpected, must be reported to the IND Office, regardless of attribution (within 5 working days of knowledge of the event).
- All life-threatening or fatal events, that are unexpected, and related to the study drug, must have a written report submitted within 24 hours (next working day) of knowledge of the event to the Safety Project Manager in the IND Office.
- Unless otherwise noted, the electronic SAE application (eSAE) will be utilized for safety reporting to the IND Office and MDACC IRB.
- Serious adverse events will be captured from the time of the first protocol-specific intervention, until 30 days after the last dose of drug, unless the participant withdraws consent. Serious adverse events must be followed until clinical recovery is complete and laboratory tests have returned to baseline, progression of the event has stabilized, or there has been acceptable resolution of the event.
- Additionally, any serious adverse events that occur after the 30 day time period that are related to the study treatment must be reported to the IND Office. This may include the development of a secondary malignancy.

## Reporting to FDA:

• Serious adverse events will be forwarded to FDA by the IND Sponsor (Safety Project Manager IND Office) according to 21 CFR 312.32.

It is the responsibility of the PI and the research team to ensure serious adverse events are reported according to the Code of Federal Regulations, Good Clinical Practices, the protocol guidelines, the sponsor's guidelines, and Institutional Review Board policy.

## 4.2 Communication between Investigator and Millennium

AEs may be spontaneously reported by the patient and/or in response to an open question from study personnel or revealed by observation, physical examination, or other diagnostic procedures. Any clinically relevant deterioration in laboratory assessments or other clinical finding is considered an AE. When possible, signs and symptoms indicating a common underlying pathology should be noted as one comprehensive event. AEs which are serious must be reported to Millennium Pharmacovigilance (or designee) from the first dose of alisertib up to and including 30 days after administration of the last dost of alisertib. Any SAE that occurs at any time after completion of alisertib treatment or after the designated follow-up period that the investigator and/or sub-investigator considers to be related to any study drug must be reported to Millennium Pharmacovigilance (or designee). Planned hospital admissions or surgical procedures for an illness or disease that existed before the patient was enrolled in the trial are not to be considered AEs unless the condition deteriorated in an unexpected manner during the trial (e.g., surgery was performed earlier or later than planned). All SAEs should be monitored until they are resolved or are clearly determined to be due to a patient's stable or chronic condition or intercurrent illness(es).

Since this is an investigator-initiated study, the principal investigator [name], , is responsible for reporting serious adverse events (SAEs) to any regulatory agency and to the investigator's EC or IRB. Regardless of expectedness or causality, all SAEs must also be reported to Millennium Pharmacovigilance or designee as soon as possible, but no later than 4 calendar days of the investigator's observation or awareness of the event. See below for contact information for the reporting of SAEs to Millennium Pharmacovigilance.

The -investigator should fax the SAE Form within four calendar days after becoming aware of the event. A sample of an SAE Form will be provided. Follow-up information on the SAE may be requested by Millennium. The SAE report must include event term(s), serious criteria, and the investigator's or sub-investigator's determination of both the intensity of the event(s) and the relationship of the event(s) to study drug administration. Intensity for each SAE, including any lab abnormalities, will be determined by using the NCI CTCAE version used at your institution, as a guideline, whenever possible. The criteria are available online at http://ctep.cancer.gov/reporting/ctc.html.

In the event that this is a multisite study, the -investigator is responsible to ensure that the SAE reports are sent to Millennium Pharmacovigilance (or designee) from all sites participating in the study. Sub-investigators must report all SAEs to so that the principal investigator can meet his/her foregoing reporting obligations to the required regulatory agencies and to Millennium Pharmacovigilance, unless otherwise agreed between the principal investigator and sub-investigator(s).

Relationship to all study drugs for each SAE will be determined by the investigator or sub-investigator by responding yes or no to the question: Is there a reasonable possibility that the AE is associated with the study drug(s)?

The principal investigator must also provide Millennium Pharmacovigilance with a copy of all communications with applicable regulatory authorities related to the study or study drug(s), including, but not limited to, telephone conversation logs, as soon as possible but no later than 4 calendar days of such communication.

SAE and Pregnancy Reporting Contact Information

Millennium Pharmacovigilance SAE and Pregnancy Reporting Contact Information:

Millennium Pharmacovigilance or Designee
SAE and Pregnancy Reporting Contact Information
[contact]
Email: [contact]

# 4.3 Procedures for Reporting Drug Exposure during Pregnancy and Birth Events

If a woman becomes pregnant or suspects that she is pregnant while participating in this study, she must inform the investigator immediately and must permanently discontinue study drug(s). The investigator must fax a completed Pregnancy Form to the Millennium Department of Pharmacovigilance or designee (or designee; see Section 4.2 for contact information) immediately. The pregnancy must be followed for the final pregnancy outcome (ie, delivery, still birth, miscarriage) and Millennium Pharmacovigilance will request this information from the investigator.

If a female partner of a male patient becomes pregnant during the male patient's participation in this study, this must be reported to Millennium Pharmacovigilance (or

designee) immediately (see Section 4.2 for contact information). Every effort should be made to follow the pregnancy for the final pregnancy outcome.

## **4.4 Product Complaints**

A product complaint is a verbal, written, or electronic expression that implies dissatisfaction regarding the identity, strength, purity, quality, or stability of a drug product. Individuals who identify a potential product complaint situation should immediately contact MedComm Solutions (see below) and report the event. Whenever possible, the associated product should be maintained in accordance with the label instructions pending further guidance from a Millennium Quality representative.

For Product Complaints, call MedComm Solutions at [contact] ([name])

(US and International)

Product complaints in and of themselves are not AEs. If a product complaint results in an SAE, an SAE form should be completed and sent to Millennium Pharmacovigilance (refer to Section 8.2).

A product complaint is a verbal, written, or electronic expression that implies dissatisfaction regarding the identity, strength, purity, quality, or stability of a drug product. Individuals who identify a potential product complaint situation should immediately contact MedComm Solutions (see below) and report the event. Whenever possible, the associated product should be maintained in accordance with the label instructions pending further guidance from a Millennium Quality representative.

A medication error is a preventable event that involves an identifiable patient and that leads to inappropriate medication use, which may result in patient harm. While overdoses and underdoses constitute medication errors, doses missed inadvertently by a patient do not. Individuals who identify a potential medication error situation should immediately contact MedComm Solutions (see below) and report the event.

### 5. STATISTICAL PROCEDURES

## 5.1 Study Design and Overview of Primary and Secondary Endpoints

The primary objective of this study is to:

• Assess 4-month disease control rate (DCR) in pre-treated patients with unresectable MPM treated with alisertib

The secondary objectives of this study are to:

- To assess the response rate (confirmed and unconfirmed complete + partial responses)
- To assess the progression-free survival.
- To assess overall survival.
- To evaluate the side effects and toxicities associated with this treatment regimen.
- To collect archival tissue, blood, pleural effusion and plasma for correlative studies.

The primary endpoint is the disease control rate at 4 months in patients with unresectable malignant pleural mesothelioma (MPM) treated with alisertib. The trial will be conducted by the Simon's minimax two-stage design and the disease control rate at 4 months will be estimated accordingly (Simon, 1989)

It is assumed that the new regimen will have a target disease control rate of 50% at 4 months. A disease control rate of 30% or lower is considered a failure and the new regimen will be rejected under this circumstance. When the probability of accepting a "bad" regimen (i.e. disease control rate<=30%) is 0.05 and the probability of rejecting a "good" regimen (i.e. disease control rate >=50%) is 0.10, Simon's minimax design requires to enter 24 patients in the first stage. If 7 or less patients are free of disease progression to the treatment at 4 months, the trial will be stopped and the regimen will be declared as ineffective. If there are 8 or more patients are alive and progression-free at 4 months, 29 more patients will be entered in the study to reach a total of 53 patients. By the end of the study, the new regimen will be rejected if disease control rate is less than or equal to 21/53 and will be accepted otherwise. The operating characteristics of the trial are given as follows. When the true disease control rate is 0.30 the probability of stopping the trial early is 57%. On the other

hand, if the true disease control rate is 0.50, the probability to stop the trial early is 3%. The expected sample sizes are 36.6 and 52.1 when the true response rates are 0.3 and 0.5, respectively. This design has the minimax property of minimizing the maximum sample size under null hypothesis. If the number of disease control required for moving the trial to the second stage has not been achieved, the patient enrollment will be halted until enough responses observed.

Descriptive statistics including mean, standard deviation, median, and range will be provided for continuous variables such as age. Frequency tables will be used to summarize categorical variables such as gender, and response. The standard error and confidence interval on estimating the disease control rate will be provided. The distribution of time-to-event endpoints, such as time to progression and overall survival, will be estimated using the method of Kaplan and Meier. Comparison of time-to-event endpoints by important patient characteristics will be made using the log-rank test. Cox proportional hazard regression will be employed for multi-covariate analysis on time-to-event outcomes when appropriate.

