#### **Statistical Procedures**

The primary objective of this study is to assess the efficacy of alisertib in pretreated patients with unresectable malignant mesothelioma (pleural or peritoneal). The primary endpoint is the disease control rate at 4 months in patients with unresectable malignant pleural mesothelioma (MPM) treated with alisertib. The trial will be conducted by the Simon's minimax two-stage design and the disease control rate at 4 months will be estimated accordingly.[2]

It is assumed that the new regimen will have a target disease control rate of 50% at 4 months. A disease control rate of 30% or lower is considered a failure and the new regimen will be rejected under this circumstance. When the probability of accepting a "bad" regimen (i.e. disease control rate<=30%) is 0.05 and the probability of rejecting a "good" regimen

(i.e. disease control rate >=50%) is 0.10, Simon's minimax design requires to enter 24 patients in the first stage. If 7 or less patients are alive and free of disease progression to the treatment at 4 months, the trial will be stopped and the regimen will be declared as ineffective. If there are 8 or more patients are alive and progression-free at 4 months, 29 more patients will be entered in the study to reach a total of 53 patients. By the end of the study, the new regimen will be rejected if disease control rate is less than or equal to 21/53 and will be accepted otherwise. The operating characteristics of the trial are given as follows. When the true disease control rate is 0.30 the probability of stopping the trial early is 57%. On the other hand, if the true disease control rate is 0.50, the probability to stop the trial early is 3%. The expected sample sizes are 36.6 and 52.1 when the true response rates are 0.3 and 0.5, respectively.

This design has the minimax property of minimizing the maximum sample size under null hypothesis. If the number of disease control required for moving the trial to the second stage has not been achieved, the patient enrollment will be halted until enough responses observed.

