# 5.7 Interim Analysis

Interim analysis will be conducted as per the Simon's 2-stage design described in Section 5.1.

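### The Section 5.1 stopping rule contradicts the Protocol Summary and leaves some stage-1 results uncovered; separately, Section 3.1 may drop early deaths from the primary count

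*Combined protocol and SAP*

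**What the plan says.** The design is Simon's minimax two-stage design with 24 patients, then 29 more to reach 53. Section 5.7 names Section 5.1 as the source of the interim rule: "Interim analysis will be conducted as per the Simon's 2-stage design described in Section 5.1".

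- **Section 5.1, stop half:** "If 7 or less patients are free of disease progression to the treatment at 4 months", then "the trial will be stopped and the regimen will be declared as ineffective".
- **Section 5.1, continue half:** "If there are 8 or more patients are alive and progression-free at 4 months", the second stage is entered.
- **Section 5.1, final rule:** "the new regimen will be rejected if disease control rate is less than or equal to 21/53 and will be accepted otherwise".
- **Section 5.1, hold (also in the Protocol Summary):** "If the number of disease control required for moving the trial to the second stage has not been achieved", then "the patient enrollment will be halted until enough responses observed".
- **Protocol Summary, Statistical Procedures, stop half:** "If 7 or less patients are alive and free of disease progression to the treatment at 4 months". Its continue half also requires patients to be alive.
- **Section 5.4:** a death is listed as progression only if it is due to disease, with no progression documented before it and no symptomatic deterioration.
- **Section 3.1:** a patient is evaluable after at least one cycle of alisertib and with a radiographic response on record. Sections 3.2 and 5.2 plan 53 evaluable patients out of at most 58, allowing for 5 inevaluable.

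**The concern.** A two-stage rule needs one count and two complementary outcomes. Section 5.1 uses two counts. A patient who dies without meeting the Section 5.4 progression definition can be read as free of progression for the stop half, yet cannot be counted as alive for the continue half. Near the boundary, neither half then applies. The hold follows, but once all 24 patients have a known 4-month status no further success can arise, and Section 5.1 gives no end to the hold. This is the trial's only efficacy stopping rule, and the choice of count would be made after the data are seen.

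The second issue is independent of the missing word. If patients who die before the first scan (about week 6) are set aside as inevaluable, failures leave the denominator and the disease control rate is biased upward, at 7/24 and at 21/53 alike.

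**Working it through.** **1. The plan's own figures.** Inputs from Section 5.1: rates 0.30 and 0.50, cut-offs 7/24 and 21/53. With one complementary count X1 ~ Bin(24, p) in stage 1 and X2 ~ Bin(29, p) in stage 2:

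- Early stop = P(X1 ≤ 7)
- Expected size = 24 + 29 × (1 − early stop)
- Acceptance = sum over x ≥ 8 of P(X1 = x) × P(X2 > 21 − x)

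| True rate | Early stop | Stated | Expected size | Stated | Acceptance |
|---|---|---|---|---|---|
| 0.30 | 0.565 | 57% | 36.62 | 36.6 | 0.0466 |
| 0.50 | 0.032 | 3% | 52.07 | 52.1 | 0.9017 |

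The design is correct. An exact search also returns 7/24 and 21/53 as the minimax choice for errors of 0.05 and 0.10.

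**2. A result that falls between the halves.** Suppose 7 of 24 are alive and progression-free, and one has died without qualifying progression.

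- Section 5.1 stop half: 7 + 1 = 8 free of progression, so it is not met.
- Section 5.1 continue half: 7 alive and progression-free, so it is not met.
- Protocol Summary stop half: 7 alive and progression-free, so the trial stops.

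**3. Size of the gap on the literal reading.** Let p be the probability of being alive and progression-free at 4 months, and d the probability of having died without qualifying progression. The documents give no value for d, so 1% to 10% is assumed. All 24 are counted.

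- Stop half as worded = P(Bin(24, p + d) ≤ 7)
- Continue half = 1 − P(Bin(24, p) ≤ 7)
- Gap = 1 − stop − continue

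| Assumed d | Stop, p = 0.30 | Continue, p = 0.30 | Gap, p = 0.30 | Gap, p = 0.50 |
|---|---|---|---|---|
| 1% | 0.522 | 0.435 | 0.043 | 0.006 |
| 2% | 0.479 | 0.435 | 0.085 | 0.012 |
| 5% | 0.358 | 0.435 | 0.207 | 0.022 |
| 10% | 0.192 | 0.435 | 0.373 | 0.030 |

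The continue column does not change with d, so the chance of opening stage 2 is unaffected. Under the Summary wording the gap is 0 in every row.

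**4. Dropping early deaths (Section 3.1).** Assume a true rate of 30% among all treated patients, and that a share e is removed because of death before the first scan. The rate among those counted is 0.30/(1 − e). The acceptance formula in step 1 then gives:

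| Assumed e | Rate among those counted | Acceptance |
|---|---|---|
| 0 | 0.3000 | 0.0466 |
| 1% | 0.3030 | 0.052 |
| 2% | 0.3061 | 0.057 |
| 5% | 0.3158 | 0.077 |

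The stated limit is 0.05. For scale, the plan allows for 5/58 = 8.6% inevaluable for any reason; it does not say how many would be deaths.

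**The case against.** The best answer is that the intent is plain. The Protocol Summary gives the same rule with the survival condition in both halves. Section 5.1 itself uses adjacent thresholds on one endpoint, and its figures reproduce only if the halves are complements. A reader may also hold that a dead patient is not free of progression at 4 months, which closes the gap without any edit. Most of this stands: it shows a dropped word, not a faulty design. It does not remove the contradiction, because Section 5.7 points to Section 5.1 and Section 5.4 expressly limits which deaths are progression.

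Three stronger readings are tempting, and the documents do not support them:

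- *The protocol states no stop for this result.* That is true of Section 5.1 only; the Summary stops.
- *The wording lets an inactive regimen through.* It does not. The continue half already requires patients to be alive, enrolment is held in the gap, and type I error is not raised. Section 6.8 also allows closure for reasonable cause, although it supplies no declaration of ineffectiveness.
- *The stated operating characteristics are wrong.* They are right for the intended count.

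It is also fair to say that the gap figures rest on assumed death rates and a literal reading, and that the Section 3.1 issue is a separate question about the analysis population.

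**Conclusion.** The concern holds as two limited points.

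**Section 5.1 wording: minor.** The operative rule contradicts the Protocol Summary and is not complementary, and the hold has no stated end. The intended rule can be recovered from the Summary. On the literal reading the gap is 4% to 37% of trials at a true rate of 30%, and at most 3% at 50%, for assumed rates of death without progression of 1% to 10%. These figures are illustrations, not forecasts.

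**Early deaths under Section 3.1: should be fixed.** If patients who die before the first scan are treated as inevaluable, the disease control rate is biased upward. Acceptance of a 30% regimen would be 0.052 to 0.077 if 1% to 5% are dropped. This assumes that the 30% applies to all treated patients and that the dropped patients would all have been failures. The documents do not say how many such deaths to expect.

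**What to change.** 1. In the Section 5.1 stop half, add the condition that patients are alive, to match the Protocol Summary.
2. Define 4-month disease control once as alive and without progression, with death from any cause before then a failure. Apply it to both 7/24 and 21/53. The progression category in Section 5.4 can stay as it is.
3. Amend Section 3.1 so that a treated patient who dies before the first scan counts as a failure in the primary analysis.
4. In the Protocol Summary and Section 5.1, replace the end of the hold, "the patient enrollment will be halted until enough responses observed", with: until the 8th success is seen or all 24 have a known 4-month status; if 7 or fewer, the trial stops.

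The numbers 24, 53, 7 and 21 do not change. Items 1, 2 and 4 are wording. Item 3 is more than wording: early deaths that would have been absorbed by the allowance of 5 become failures. A 4-month status must also be ensured for patients off treatment. Section 3.8 says they are followed for first progression and survival, but footnote d of the Schedule of Events provides only chart review or telephone contact at 30 days after treatment, at 3 months and then every 6 months.

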Analysis of efficacy results will be conducted using standard statistical methods. Descriptive statistics including mean, standard deviation, median, and range will be provided for continuous variables such as age. Frequency tables will be used to summarize categorical variables such as gender, and response. The standard error and confidence interval on estimating the disease control rate will be provided. The distribution of time-to-event endpoints, such as time to progression and overall survival, will be estimated using the method of Kaplan and Meier. Comparison of time-to-event endpoints by important patient characteristics will be made using the log-rank test. Cox proportional hazard regression will be employed for multi-covariate analysis on time-to-event outcomes when appropriate.

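### Does the plan need to name the estimator, interval method and confidence level for the 4-month disease control rate?

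*Combined protocol and SAP*

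**What the plan says.** Section 5.1 sets out a Simon minimax design with 24 patients in stage 1, stopping at 7 or fewer successes, and 53 in total. The final rule is that "the new regimen will be rejected if disease control rate is less than or equal to 21/53 and will be accepted otherwise". The error rates are attached to the two design rates: the probability of accepting a poor regimen ("disease control rate<=30%) is 0.05") and of rejecting a good one ("disease control rate >=50%) is 0.10").

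On estimation, Section 5.1 says that "the disease control rate at 4 months will be estimated accordingly", where the reference is to the two-stage design. Section 5.4 and the Statistical Procedures part of the Protocol Summary say the same. Section 5.1 adds that "The standard error and confidence interval on estimating the disease control rate will be provided", and Section 5.6 repeats this. The summary also says "Analysis of efficacy results will be conducted using standard statistical methods". Section 5.7 only points back to Section 5.1. Nowhere do the documents name an estimator, an interval method, a confidence level, or one-sided versus two-sided.

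**The concern.** The disease control rate and its interval are the trial's main numerical result, and two analysts following this text could report different figures. Two consequences look troubling.

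First, if the text is read as the ordinary binomial proportion, that estimate is not unbiased after a two-stage trial. Stopping for poor results fixes low stage 1 estimates in place, while promising ones are diluted by further data, so the average over all outcomes falls below the truth.

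Second, the accept rule is in effect a one-sided 5% test against 30%. If the report used a two-sided 95% interval (an assumption, since the plan gives no level), it could declare the regimen accepted beside an interval that still contains 30%. A choice of method made after seeing the count could also change the message: at 23/53 some 95% intervals exclude 30% and others do not.

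**Working it through.** **Inputs (Section 5.1).** Stage 1 n1 = 24, stop at 7 or fewer; stage 2 adds 29, total 53; accept at 22 or more; design rates 0.30 and 0.50; error limits 0.05 and 0.10.

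**Step 1: reproduce the design.** With X1 ~ Bin(24, p) and X2 ~ Bin(29, p):

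- P(stop) = P(X1 ≤ 7)
- P(accept) = Σ over x1 ≥ 8 of P(X1 = x1) · P(X2 ≥ 22 − x1)
- Expected size = 24 + 29 · [1 − P(stop)]

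| True rate | P(stop) | P(accept) | Expected size |
|---|---|---|---|
| 0.30 | 0.5647 | 0.0466 | 24 + 29 × 0.4353 = 36.6 |
| 0.50 | 0.0320 | 0.9017 | 24 + 29 × 0.9680 = 52.1 |

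These agree with the plan, which prints 57% for the first stopping probability (56.5% exactly, a rounding matter). The estimate and the interval enter none of these formulas.

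**Step 2: bias and error of the point estimate.** The simple proportion is x/24 if the trial stops and s/53 otherwise. The uniformly minimum variance unbiased estimator (UMVUE) equals x/24 at stage 1. At stage 2 it is Σ C(23, x−1)·C(29, s−x) / Σ C(24, x)·C(29, s−x), with both sums over x ≥ 8. Exact expectations, in percentage points:

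| True rate | Bias, all outcomes: simple / UMVUE | Bias given stage 2: simple / UMVUE | RMSE: simple / UMVUE |
|---|---|---|---|
| 30% | −2.0 / 0 | +3.9 / +8.6 | 7.8 / 8.8 |
| 40% | −1.5 / 0 | +1.5 / +3.4 | 8.6 / 8.2 |
| 50% | −0.4 / 0 | +0.3 / +0.8 | 7.7 / 7.3 |

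The two estimators coincide when the trial stops early, so they differ only in a trial that reaches stage 2. The difference there is 42.8 − 41.5 = 1.3 points at 22/53, 0.2 at 26/53, and below 0.01 at 30/53.

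**Step 3: intervals near the cut-off.** Lower limits, to be compared with 30%:

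| Method | 22/53, 95% | 22/53, 90% | 23/53, 95% |
|---|---|---|---|
| Clopper-Pearson | 28.1% | 30.03% | 29.8% |
| Two-stage exact | 28.3% | 30.2% | 29.9% |
| Wald | 28.2% | 30.4% | 30.05% |
| Wilson | 29.3% | 31.1% | 31.0% |

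Every 95% method includes 30% at 22/53, the two-stage one among them. The cause is therefore the pairing of a one-sided 5% test with a two-sided 95% interval, not neglect of the stopping rule.

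**Step 4: how often a 95% interval would include 30% after acceptance.** With Wald or Wilson only the count 22 is affected; with the exact methods 22 and 23 are.

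- True rate 50%: P(22) = 0.0471, P(23) = 0.0656. Share of accepting trials: 0.0471/0.9017 = 5.2%, or (0.0471 + 0.0656)/0.9017 = 12.5%.
- True rate 40%: P(22) = 0.0989, P(23) = 0.0920, P(accept) = 0.4448. Share: 22%, or 43%.

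**Step 5: coverage.** Ordinary 95% Clopper-Pearson intervals, evaluated over the two-stage distribution, cover at 97.5%, 96.4% and 96.8% for true rates of 30%, 40% and 50%. At the 90% level, coverage is 91.0% at a true rate of 30% and 88.3% at 50%; a two-stage exact 90% interval gives 91.1% and 90.2%.

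**The case for a change.** The case for a change is that the primary endpoint's estimator and interval should be fixed before the data are read, and one sentence would do it: for example, the UMVUE with a two-stage exact 90% interval, which matches the accept rule at both 21/53 and 22/53. The omission is real, the arithmetic holds, and the choice of method does alter what is shown at 23/53. It is also true that the reference to Simon's design does not itself name an estimator.

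What does not stand is the step from omission to defect. The interval has no part in the decision, so one that contains 30% contradicts no rule in the plan. The same thing happens at the boundary of any one-sided 5% test reported with a two-sided 95% interval.

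Nor is the proposed replacement plainly better. The UMVUE removes a bias averaged over all outcomes, but roughly doubles the upward bias among trials that continue. Which criterion should govern is a matter of judgement. The largest overall bias (2.0 points at 30%) arises where 56% of trials stop early and fewer than 5% accept. A 90% interval matches the test but gives up the customary level, and its ordinary version slips to 88.3% coverage at the target rate. Preferring 90%, or a 95% interval read as descriptive, is a reporting convention on which statisticians reasonably differ.

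**Conclusion.** No change is needed. The plan leaves the estimator, method and level open, but a competent analyst fills that gap without harm. The ordinary proportion with an exact 95% interval is conservative at the rates of interest, and a two-stage estimate and interval are equally compatible with the plan's wording. The choice moves the point estimate by at most 1.3 points among accepted counts, and the 90% interval at 22/53 is about 24 points wide (30.03% to 53.7%, ordinary exact). Type I error, power and the accept rule do not move.

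The visible mismatch between a 95% interval and acceptance would occur in 5% to 12.5% of accepting trials at a true rate of 50%, and 22% to 43% at 40%, depending on the method. It rests on the assumption of a two-sided 95% level, which the documents do not state. A reader who meets it needs only to know that the test is one-sided. All figures assume that exactly 24 and 53 patients are counted and that each patient's 4-month status is known.
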